#### Pregnancy test procedures

At the baseline home visit, after consent is obtained from both partners, we will conduct a pregnancy test. Though the eligibility screening questions asks women if they are currently pregnant, we will conduct the test to confirm. The consent form will inform women that if the pregnancy test is positive, they will not be able to continue participation in the study. The pregnancy test will be a Human Chorionic Gonadotropin (HCG) urine test strip, which requires the woman to urinate in a cup (provided by research staff) and immerse the strip in the cup vertically. The woman will be instructed to urinate in the cup by the research assistant and bring the cup to the research assistant afterward and will be given privacy to do so. The research assistant will immerse the strip in the cup and will read the woman her results (~10 minutes later). If the woman is unable to urinate at the time, the research assistant will schedule a time to return to conduct a second test. If the results are invalid, the research assistant will immerse the strip for longer, conduct a second test, or schedule a time to return to conduct a second test. If the pregnancy test is negative (our final eligibility criterion), the research assistant will conduct the baseline questionnaire with each partner separately either in the home or another agreed upon location. The research assistant will ensure that each partner in the couple have full privacy when completing the questionnaire. If they do not, the research assistant will reschedule the interview for another time. During the 6-month follow-up visit, women fill follow these same procedures. The 6-month visit pregnancy test is used to measure change in incidence of unintended pregnancies. The pregnancy test results will be double entered by the research assistant into a KoboCollect data file upon receipt.

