#### Data collection

#### Questionnaires

**Baseline.** After the informed consent process in a one-on-one interview, using a computerized structured questionnaire in the participant's home or another agreed upon location, the Research Assistants will collect demographic information and the measures to assess family planning determinants. Participants can also complete the baseline interview over the phone shortly after enrollment if needed. Total duration ~45 minutes.

- **~7-month assessment**. Research Assistants will conduct a ~7-month follow up with the interviewers using an individual structured interviewer-administered computer-based interview (~45 minutes duration) in the participant's home, another agreed upon location, or via telephone. The 7-month questionnaire will serve as a measure of intervention effects on contraceptive use and relevant determinants of family planning. Total duration ~45 minutes.
- **~10-month assessment**. At ~10-month follow-up the interviewers will conduct an individual structured computer-based interview (~45 minutes duration) in the participant's home or another agreed upon location. Men and women may complete this survey via telephone; however, women must complete a second pregnancy test in-person. The 10-month questionnaire will serve as a measure of intervention effects on contraceptive use, contraceptive continuation, and relevant determinants of family planning. Total duration ~45 minutes (55 minutes for women taking pregnancy test)

\*Note: The study protocol originally planned for 3 and 6-month follow-up time points, but the assessment points were extended due to COVID-19 travel restrictions that occurred during the study.

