### Women found pregnant at baseline

If pregnant, the research assistant will inform the woman of the test results alone, unless the woman prefers for them to be delivered with her husband present. The research assistant will then provide brief couples counseling on the importance of prenatal care, having a skilled attendant at birth, and breastfeeding, provide an information sheet with a list of nearby health facilities offering free prenatal care, and a paper referral to the couples' preferred health facility. She and her partner will be withdrawn from the study and informed of their withdrawal.

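### At the final follow-up, the only written order gives the pregnancy test result before the questionnaire on contraceptive use

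*Combined protocol and SAP*

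**What the plan says.** In the combined protocol and SAP, the Pregnancy test procedures section describes the baseline visit in full. After consent the woman provides urine, and the research assistant immerses the strip and "will read the woman her results (~10 minutes later"). The consent form warns that "if the pregnancy test is positive, they will not be able to continue participation in the study". The interview then follows: "If the pregnancy test is negative (our final eligibility criterion), the research assistant will conduct the baseline questionnaire with each partner separately".

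For follow-up the section adds only "During the 6-month follow-up visit, women fill follow these same procedures" and a statement of purpose: "The 6-month visit pregnancy test is used to measure change in incidence of unintended pregnancies". The Questionnaires section explains that the planned 3- and 6-month assessments were moved to about 7 and 10 months, so the 6-month label refers to what is now the 10-month visit.

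For that visit the Questionnaires section says: "Men and women may complete this survey via telephone; however, women must complete a second pregnancy test in-person". It gives the duration as about 45 minutes, or 55 for women who are tested. It describes no pregnancy test at about 7 months. Both follow-up questionnaires measure contraceptive use.

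The Data Analysis Plan names contraceptive uptake as the main outcome, tested through the time-by-intervention interaction in a GEE logit model. Unintended pregnancy is reported descriptively.

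**The concern.** At baseline the test is an eligibility check, so it makes sense to do it before the interview. At the last visit the test measures an outcome, and the interview measures contraceptive use and other family planning determinants. Carrying the baseline sequence over puts disclosure of one outcome just before self-report of another that is closely tied to it.

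A woman who has just learned that she is pregnant, or that she is not, may describe recent use, continuation and intentions differently. The research assistant role that reads the strip is also the one that interviews, so the interviewer need not be unaware of the result. Couples enter the trial using no method or a low-efficacy one (Inclusion criteria, item 9), so positive tests at follow-up are foreseeable. If some women answer by telephone before the test and others in person after it, the exposure also differs between participants in a way that nobody is asked to record.

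**Working it through.** The documents give no figure for this point, so there is none to reproduce. The check compares the sections.

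**1. Which order is written?** The baseline order is urine, strip, result at about 10 minutes, questionnaire. The follow-up sentence refers back to it, and no section gives a different follow-up order. The only written sequence therefore discloses the result first.

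**2. Does the Questionnaires section settle the order?** No. The visit lasts 45 minutes, or 55 with the test, and 55 − 45 = 10 minutes, which matches the strip wait. This suggests that test and interview are done back to back at one visit, but not which comes first. The telephone option separates the two for some women, again with no order.

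**3. Which assessments are exposed?** Only the 10-month one. No test is described at 7 months, so contraceptive use reported there is unaffected.

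**4. What happens after a positive follow-up test?** No section says. The withdrawal rule, "She and her partner will be withdrawn from the study and informed of their withdrawal", stands under the heading "Women found pregnant at baseline". The Data Analysis Plan gives no rule for counting a pregnant woman in uptake.

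**5. Size.** The effect of disclosure on answers needs a figure that the documents do not give, and its direction is not known either. What can be illustrated is a different case: the effect if test-positive women were in fact not interviewed. All inputs are assumptions, and pregnant women are counted as non-users.

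- Let u be true uptake and r the share of non-users who are pregnant and not interviewed. Observed uptake = u / [u + (1 − u)(1 − r)].
- u = 60% v 30%, r = 20% in both arms: 60/(60 + 32) = 65.2% v 30/(30 + 56) = 34.9%, about 5 points too high in each arm. The odds ratio is (60/32)/(30/56) = 3.5, equal to the true (60/40)/(30/70) = 3.5.
- Same uptake, r = 10% (intervention) v 20% (control): (60/36)/(30/56) = 3.11.
- Now let q be the share of the whole arm that is pregnant, so observed uptake = u/(1 − q). With u = 50% v 30% (20.0 points, odds ratio 2.33):
  - q = 5% in both arms: 21.1 points, odds ratio 2.41.
  - q = 5% v 20%: 0.50/0.95 = 52.6% v 0.30/0.80 = 37.5%, 15.1 points, odds ratio 1.85.
- Couples lost, assuming 35 per arm (the 70 intervention participants in Process Data, counting both partners): in the equal-risk case 0.08 × 35 = 2.8 v 0.14 × 35 = 4.9; in the 5% v 20% case 0.05 × 35 = 1.75 v 0.20 × 35 = 7.

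So under that reading the contrast could be unchanged, slightly inflated or pulled toward no effect, depending on pregnancy rates that the documents do not give.

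**The case against.** A reader might infer that pregnant women receive no questionnaire at the last visit, because the written sequence reaches the questionnaire only after a negative test. The documents do not support this as a stated exclusion. The negative-test condition is labelled an eligibility criterion and governs the baseline questionnaire. Withdrawal is headed as applying to women pregnant at baseline. The follow-up test is itself an outcome measure, so a positive result is data. The 55-minute duration for tested women carries no condition on the result. This objection stands. What remains is a gap: no instruction covers a positive follow-up test, and the cross-reference exempts no step.

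A reader might also infer that the result always comes before the interview. That is too strong. The cross-reference stands under a heading about the test and can be read as covering only the cup, strip and result. The telephone option separates survey and test, and a test may be rescheduled if the woman cannot urinate or the strip is invalid. Disclosure first is therefore the only order written, not a fixed rule for every woman.

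Exposure is limited as well. The analysis plan does not single out the last visit, and clinic record abstraction (Quantitative data section) captures the method received without relying on the interview, although nothing says that it defines the main outcome. Finally, the Data Analysis Plan is written in the past tense, so rewording the protocol may come too late to change the data.

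**Conclusion.** The point holds as a risk of bias at the 10-month assessment. Where test and interview share a visit, following the text as written lets the woman and her interviewer know the result before she reports contraceptive use. For women surveyed by telephone the order is unspecified. The size and direction of any bias cannot be derived from the documents. The odds ratios above do not measure it; they apply only if test-positive women were left out of the questionnaire, which is probably not intended, and they rest entirely on assumed rates. The 7-month assessment is not affected. The conclusion assumes that field staff follow the one sequence on the page and that the main outcome rests on the questionnaire, as the Questionnaires section indicates.

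**What to change.** Replace the cross-reference with a separate follow-up paragraph under the current 10-month label, stating that:

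- the questionnaire is completed first; then urine is collected and the strip is immersed and read at its usual 10 minutes or so, so the reading time does not change;
- where the survey is by telephone, the call comes before the test where possible, and the order is recorded;
- both partners complete the questionnaire whatever the test result.

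If data are already collected, report the order actually used and the number of test-positive women without a 10-month questionnaire, by arm.

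The cost is a short paragraph and one recorded item. No visit, test or staff is added. The downside is that the woman learns her result about 45 minutes later.

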#### Inclusion criteria

- 1) Married or considers themselves married
- 2) Living with partner most of the time
- 3) Living within the selected villages in the last 3 months
- 4) Age 18 (or an emancipated minor) to 40 for women; age 18 to 50 for men
- 5) Luganda speaking
- 6) Not currently pregnant
- 7) Has no knowledge of infertility
- 8) Wanting to avoid pregnancy for at least a year (at least one person in the couple)
- 9) Not using a method of contraception at the moment OR only using low-efficacy or ineffective method of contraception (defined as using condom less than 100% of the time, Fertility-Awareness Based methods e.g., counting method, withdrawal method, spermicide, emergency contraception, and sponge)
- 10) Never used a non-reversible method (male or female sterilization)
- 11) Has sex in the past 3 months (woman)

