## Recruitment & Sampling

In each village, members of the Village Health Team (VHT) will assist our research staff in identifying potentially eligible couples. For the couples that we attempt to recruit based on the VHT's referral, the VHT will first independently visit couples' homes to introduce them to the study, and gain permission to return with the research assistant. If permission is granted, the VHT will accompany our research assistant to couples' homes to introduce our research assistant.

If both partners are together during this initial meeting, the research assistant will inform them of the overall study together, but will screen and assess eligibility separately, ensuring that participants are able to answer the eligibility screening questions about fertility preferences and current use of contraceptives in a private setting to ensure confidentiality. Research assistants will be trained in to try to separate spouses in a culturally appropriate and sensitive manner. In cases where the research assistant feels separate screening will not be possible, s/he will attempt to reschedule to come back and conduct the screenings separately. If a reschedule is not possible and screening must happen together, the research assistant will conduct a follow-up phone call or house visit with just the woman to confirm the accuracy of her responses. The research assistant will then obtain written informed consent from the participants. See recruitment script for eligibility screening questions. No identifying information will be collected for eligibility screening. The interviewer will proceed to conduct the baseline questionnaire after obtaining written informed consent for both partners.

If only one partner is present during the initial meeting, the research assistant will proceed with the eligibility screening. If the partner (male or female) is found eligible and interested, the research assistant will ask him/her to refer their partner to the study (either by calling their partner themselves, having the partner call the research assistant or the VHT). The research assistant will conduct the eligibility screening with the second partner over the phone, or will return to the house at the scheduled date and time, and follow the same procedures described above to assess eligibility, obtain informed consent for study participation, and conduct the baseline questionnaire.

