## Data Analysis Plan

We assessed baseline equivalence between the study arms on demographics using Generalized Estimating Equation (GEE) models in SPSS v. 28, which account for dependence from repeated, dyadic data. We tested intercorrelations between variables that differed (p < 0.10) between arms at baseline, or variables deemed theoretically relevant (i.e., age, number of children), to identify covariates. Based on these analyses, all models controlled for religion (based on differences in baseline equivalence) and age. The time by intervention interaction on contraceptive uptake (main outcome) at follow-up was tested using GEE with a logit link distribution (couple the unit of analysis). We report unintended pregnancy descriptively (underpowered but included for feasibility). For all secondary outcomes, GEE was used (linear for continuous outcomes and logistic for binary outcomes), with time and gender specified as within-subject effects. Unstandardized betas (b) and standard errors (SE) are reported for continuous outcomes and adjusted odds ratios (AORs) and 95% confidence intervals (CIs) are reported for binary outcomes.

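### The follow-up urine test is named as the measure of unintended pregnancy with no intention item attached, and criterion 8 admits couples in which one partner may want a pregnancy, so a positive test alone can label a wanted pregnancy as unintended.

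*Combined protocol and SAP*

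**What the plan says.** Four parts of the combined protocol and SAP bear on this.

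- **Pregnancy test procedures** names the instrument and the outcome together: "The 6-month visit pregnancy test is used to measure change in incidence of unintended pregnancies". The visit label is a remnant of the old schedule. Under Questionnaires, the test now belongs to the visit at about 10 months, where "women must complete a second pregnancy test in-person".
- **Inclusion criteria, item 8** sets the entry rule on intention: "Wanting to avoid pregnancy for at least a year (at least one person in the couple". Nothing is required of the other partner.
- **Recruitment & Sampling** has each partner answer "eligibility screening questions about fertility preferences and current use of contraceptives in a private setting", and adds: "No identifying information will be collected for eligibility screening". Under **Questionnaires**, the baseline interview is to "collect demographic information and the measures to assess family planning determinants"; the items are not listed.
- **Data Analysis Plan** gives the outcome one sentence: "We report unintended pregnancy descriptively (underpowered but included for feasibility". It does not define the term or give a rule for classifying a pregnancy.

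**The concern.** The named measure and the named outcome are different things. The test gives pregnant or not pregnant. To call a pregnancy unintended, one must also know what the woman, her partner, or both wanted when it was conceived.

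Had criterion 8 required both partners to want to wait, a positive test within the year could reasonably have stood in for an unintended pregnancy. Because one partner is enough, that shortcut fails for couples who disagree. If the man wants to wait and the woman conceives on purpose, the label contradicts her wish. If the woman wants to wait and the man does not, the label fits her but not him. The plan does not say which view decides.

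For a descriptive outcome, the count and its label are the whole result. The plan includes this one for feasibility. A rate that contains an unknown share of wanted pregnancies would mislead anyone who later took it as the rate of unintended ones.

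**Working it through.** The plan states no pregnancy rate, no share of discordant couples and no power for this outcome, so there is no figure to reproduce. The check is mainly one of reading, followed by an illustration.

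**Step 1. What a positive test means, by type of couple admitted under criterion 8**

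| Woman wants to wait | Man wants to wait | Eligible on item 8 | What a positive test shows about intention |
|---|---|---|---|
| Yes | Yes | Yes | Consistent with unintended, unless wishes changed |
| Yes | No | Yes | Unintended for her, not necessarily for him |
| No | Yes | Yes | May be wanted by her |
| No | No | No | Not applicable |

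Two of the three eligible types need an intention answer before the pregnancy can be classified.

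**Step 2. Does the plan supply that answer?** Fertility preferences are asked at screening, but no link from screening to the test result is described. The questionnaires may hold such an item, but their contents are not listed. The Quantitative data section says only that test results are double entered. Neither the test section nor the Data Analysis Plan combines the result with anything else.

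**Step 3. Does timing matter?** Criterion 8 looks a year ahead and the test falls at about 10 months, inside that window. The extended follow-up therefore adds little. The point rests on discordant couples.

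**Step 4. Illustration; none of these inputs is in the documents.** Let *s* be the share of couples in which the woman wants a pregnancy, and *r* their risk of pregnancy relative to the other couples. The share of positive tests that are not unintended from the woman's standpoint is

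s·r / (1 − s + s·r)

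- s = 0, wishes unchanged: 0%
- s = 10%, r = 1: 0.10 / 1.00 = 10%
- s = 10%, r = 3: 0.30 / 1.20 = 25%
- s = 20%, r = 2: 0.40 / 1.20 = 33%
- s = 30%, r = 1: 0.30 / 1.00 = 30%
- s = 30%, r = 3: 0.90 / 1.60 = 56%

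A second set of assumptions starts from all discordant couples. If 10% of couples are discordant with relative risk 1.5, they supply 0.15 / 1.05 = 14% of positive tests. If 30% are discordant with relative risk 2, they supply 0.60 / 1.30 = 46%. If the woman is the one wanting a pregnancy in half of them, and both kinds of discordant couple conceive equally often, the mislabelled share is 7% to 23%.

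**Step 5. Effect on the comparison of arms.** Suppose wanted pregnancies add the same risk *w* to both arms, whose unintended risks are p₁ and p₀. The risk difference is (p₁ + w) − (p₀ + w) = p₁ − p₀, which is unchanged. Both rates are inflated, and the ratio (p₁ + w) / (p₀ + w) moves towards 1.

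**The case against.** The strongest reply is that the documents are silent rather than wrong, and that several tempting readings go further than the text.

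- A reader might infer that every positive test is to be counted as unintended. No section states that rule. Using a test to measure an outcome is compatible with combining it with interview answers.
- A reader might infer that intention is never collected. The interviews run to about 45 minutes with each partner, their items are not listed, and the screening questions sit in a recruitment script outside the document. Intention may be in either.
- A reader might infer that screening answers cannot be linked to the test. Collecting no identifying information does not rule out a study ID; the Quantitative data section uses one for clinic records, and screening and baseline can take place at the same home visit.
- A reader might infer that the outcome cannot be measured at all. It can, if the test is paired with recorded intention.
- The result is reported only descriptively and is declared "underpowered but included for feasibility".

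All of this stands, and it limits the point. It does not remove it. The test is the only measure the plan names for this outcome, the entry rule does not supply the missing intention, and no section says how intention enters the count or whose it is. It is also fair to say that, in a trial of couples, counting by the woman's intention alone would be a choice of definition. That is a reason to show both partners' answers.

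**Conclusion.** The point holds as a mismatch between measure and outcome. Followed as written, the plan allows a wanted pregnancy to be reported as unintended. It does not require this for every positive test, and it does not show that intention data are absent.

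The size cannot be determined. It is near zero if few couples are discordant and wishes do not change. The illustrations of 10% to 56% and 7% to 23% rest wholly on assumed discordance and assumed relative risks; they show the mechanism and are not evidence about this trial. The expected risk difference between arms is preserved if wanted pregnancies are equally common in both.

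The consequence is confined to one descriptive outcome. The main analysis, contraceptive uptake, is untouched. The correction is still worth making, because the label is the substance of what will be reported and putting it right is cheap.

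**What to change.** 1. In Pregnancy test procedures, state that the strip measures pregnancy, and place it at the visit at about 10 months to match the current schedule.
2. In the Data Analysis Plan, report all pregnancies by arm. On a separate line, report unintended pregnancies, defined by a positive test plus linked intention data. Show the woman's and the partner's answers separately, and split couples by whether one or both partners met criterion 8.
3. For the intention data, use items already held under the study ID. If data collection is still open, add one item per partner to the planned interviews. The Data Analysis Plan is written in the past tense and the schedule note describes events during the study, so this may no longer be possible.
4. If no linked intention data exist, rename the outcome as any pregnancy at about 10 months and state that intention was not classified.

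The cost is two table lines and, at most, one short question per partner; renaming costs only the edit. The downsides are small: the unintended count may fall, and intention asked after conception is open to recall bias, which any linked baseline answer would help to check.
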